- ORR, DOR, and PFS based on HPV status and PD-L1 expressions (combined positive score [CPS] ≥ 1 and CPS ≥ 20)

Exploratory Endpoints:

- Response in injected and noninjected target lesions per intratumoral Response Evaluation Criteria in Solid Tumors (itRECIST) by Investigator assessment
- Baseline, and change from Baseline, in tumor or blood measurements of biomarkers related to TLR9, immune checkpoints, and potential markers of resistance or response to immunotherapy
- Change from Baseline in blood concentrations of C-X-C motif chemokine 10 (CXCL10) (IP-10) and other cytokines after treatment with CMP-001
- Blood concentrations of CMP-001 or its metabolites

Methodology:

This is a multicenter, open-label, Phase 2 clinical trial of CMP-001 administered by IT injection in combination with intravenous (IV) pembrolizumab in subjects with recurrent or metastatic head and neck squamous cell carcinoma (HNSCC) not previously treated with a PD-1 blocking antibody. This will be a Phase 2 study, with response and DOR assessments using RECIST v1.1 and iRECIST criteria according to Investigator assessment. All subjects will receive CMP-001 IT and pembrolizumab IV according to the treatment schedule until a reason for treatment discontinuation is reached.

Number of subjects (planned):

A total of 43 subjects is planned for this study. This is based on the following assumptions:

- A historical ORR of 19% with pembrolizumab monotherapy in subjects with HNSCC who have a CPS ≥ 1 and were not previously treated with a PD-1 blocking antibody (null hypothesis)
- An anticipated ORR of 35% with CMP-001 and pembrolizumab (alternative hypothesis).
- Power of 80% and one-sided alpha level of 0.05.

Diagnosis and main criteria for inclusion:**Inclusion criteria:**

Subjects enrolled in the study must meet all of the following inclusion criteria to be eligible:

1. Subjects with histologically- or cytologically-confirmed recurrent or metastatic HNSCC considered incurable by local therapies, and subjects with T4 or N3 disease who are ineligible for or refusing local therapies.
2. No prior systemic therapy in the recurrent or metastatic setting. Systemic therapy as part of multi-modal treatment for locally advanced disease is allowed.
3. Primary tumor locations of oropharynx, oral cavity, hypopharynx, larynx, paranasal sinus, or HNSCC of unknown primary origin. Participants may not have a primary tumor site of nasopharynx (any histology).

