C. Sample Size Status

Given the early termination of site activation and study enrollment since 24Jun2022 per Sponsor's decision, all the analyses will be descriptive and exploratory. The number of subjects included in this study is 24. Subjects who have provided written informed consent once the enrollment goal is reached may be allowed to complete Screening and enter study treatment if they meet all eligibility criteria, at the discretion of the Sponsor or its representatives. As enrollment is terminated, subjects who discontinue the study before receiving the first dose of CMP-001 will not be replaced.

With the enrollment of the last subject on 22Jun2022, the subject status of this study is as follows:

- 39 subjects were screened
- 15 subjects were screen failures
- 24 subjects started the treatment

D. Treatment Randomization

No randomization will be performed in this study.

E. Assessment Schedule

See Protocol Table 1 for the study schedule of assessments.

F. End of Study

Per Sponsor's decision, site activation and study enrollment were terminated officially on 24Jun2022. All subjects previously enrolled in the study may continue receiving up to 2 years of study treatment per the current protocol.

The end of study is defined as the date of the last dose of study treatment for the last ongoing subject, plus 30 days of safety follow-up.

III. Protocol Objectives

Per Sponsor's decision, enrollment was stopped before reaching the sample size planned for the analyses described in the Protocol. All analyses will be exploratory. The performance of the statistical analysis for the protocol objectives and endpoints of the exploratory phase 2 study is contingent on the availability of the data source. Detailed information will be provided in the corresponding sections to follow.

Regeneron Pharmaceuticals Inc. / Protocol: CMP-001-007
IQVIA Biotech (Confidential) Project # SZA56629

A. Primary

- To determine the Investigator-assessed confirmed objective response with CMP-001 in combination with pembrolizumab in subjects with head and neck squamous cell carcinoma (HNSCC).

B. Secondary

- To evaluate the safety and tolerability of CMP-001 administered by intratumoral (IT) injection in combination with pembrolizumab in subjects with HNSCC.
- To evaluate the efficacy of CMP-001 in combination with pembrolizumab in subjects with HNSCC.

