 - ORR, DOR, TTR, PFS per RECIST v1.1 by Investigator
 - OS
 - Selected subgroup analysis
- Safety
 - Study drug exposure: CMP-001 and pembrolizumab
 - Prior and concomitant medications
 - Prior and concomitant procedures
 - All TEAEs (SAE, AESI)
 - Summary of clinical laboratory results
 - Summary of ECG results

H. Multiple Comparisons

No control for the effect of multiple comparisons is planned.

I. Analysis Sets

Three analysis sets will be defined for use with various analyses. The following table illustrates the relationship between each population and the analyses for which the data from the population will be used.

Regeneron Pharmaceuticals Inc. / Protocol: CMP-001-007
 IQVIA Biotech (Confidential) Project # SZA56629

Analysis Set	Analysis					
	Baseline	Subject Disposition	Efficacy	Safety	PD	Tumor Biopsy
Treated	X	X	X	X		
Pharmacodynamic					X	X
All Screened		X				

1. Treated Analysis Set

The Treated Analysis Set is defined as all subjects who receive at least 1 dose of study treatment.

2. Pharmacodynamic Analysis Set

The Pharmacodynamic Analysis Set is defined as all subjects who receive at least 1 dose of CMP-001 and have at least 1 measurable sample at Baseline and at least 1 evaluable biomarker sample after CMP-001 administration.

3. All-Screened Analysis Set

The All-Screened Analysis Set is defined as all subjects who was screened including subjects who were screen failure.

J. Subgroups of Analysis Populations

1. HPV Status

- Negative
- Positive

2. PD-L1 Expression (Combined Positive Score, CPS)

- $1 \leq \text{CPS} < 20$
- $\text{CPS} \geq 20$

3. Schedule

- A: Subjects under Schedule A are those who consented to protocol v1.0 and v2.0.
 - Per Protocol, subjects will receive CMP-001 10 mg weekly for 7 doses, after which CMP-001 will be administered every 3 weeks (Q3W), beginning on Week 10 Day 1 (W10D1), then on Week 13 Day 1 (W13D1), etc.
 - Subjects will receive Pembrolizumab 200 mg IV over 30 minutes following CMP-001 injection at Week 1 Day 1 (W1D1) and every 3 weeks thereafter (W4D1, W7D1, etc.) according to the

Regeneron Pharmaceuticals Inc. / Protocol: CMP-001-007
IQVIA Biotech (Confidential) Project # SZA56629

KEYTRUDA® (pembrolizumab) United States Prescribing Information. Pembrolizumab should be administered until the subject satisfies a condition for study treatment discontinuation.

- B: Subjects under Schedule B are those who consented to protocol v3.0, including those who reconsented to v3.0 from v2.0.

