Subgroup analysis for ORR, DOR, and PFS based on HPV status (Positive vs. Negative) and PD-L1 expressions (combined positive score [CPS] ≥ 1 vs. CPS ≥ 20) for the Treated Analysis Set will be performed using the same approach for the main analysis. Additionally, subgroup analysis of ORR, DOR and OS by schedule will also be performed.

The following efficacy figures will be generated using the Investigator reported RECIST v1.1 assessments on the Treated Analysis set. Additional figures for the iRECIST by Investigator assessments may be produced.

- A waterfall plot of best percent change in the tumor burden of injected and non-injected target lesions from the Screening/Baseline target lesion assessment for each subject.
 - Tumor burden as reflected by the sum of the diameters (SOD) of all target lesions, concerning longest diameters for extranodal lesions and short axis for lymph nodes, will be assessed at baseline and at each disease assessment after the first dose of CMP-001.
 - Tumor burden change will be calculated as the percentage change in SOD of target lesions from baseline for each efficacy evaluable subject at each disease assessment.
 - The waterfall plot will display each BOR category as a separate color.
- A spider plot of the percent changes in the tumor burden of target lesion measurements (including the sum of diameters (SOD) of all target lesions, the longest diameters for extranodal lesions, and the short axis for lymph nodes) from the Screening/Baseline target lesion assessment over time.

Regeneron Pharmaceuticals Inc. / Protocol: CMP-001-007
IQVIA Biotech (Confidential) Project # SZA56629

- The spider plot will display each BOR category as a separate color.
- A swimmer plot delineating the occurrence of the clinical outcomes of interest over time, including the following information:
 - Duration on study treatment
 - Time to BOR based on RECIST v1.1 as assessed by Investigator, except that PD will be the first occurrence of PD. The swimmer plot will display each Confirmed BOR category as a separate color.
 - Time to death
 - The swimmer plot will display each BOR category as a separate color.
- Kaplan-Meier plots displaying time-to-event on TTR, DOR, PFS, OS per RECIST v1.1 as assessed by Investigator:
 - Estimate of median and the corresponding two-sided 95% CIs for median
 - Event-free rates at selected timepoints

D. Exploratory Efficacy Analysis

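### Time to response is listed for a Kaplan-Meier plot in the Treated Analysis Set without a definition, risk set or censoring rule; read as written, the curve would usually overstate the chance of responding

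*SAP*

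**What the plan says.** The figure list in SAP VIII.C opens with "The following efficacy figures will be generated using the Investigator reported RECIST v1.1 assessments on the Treated Analysis set". Its last item is "Kaplan-Meier plots displaying time-to-event on TTR, DOR, PFS, OS per RECIST v1.1 as assessed by Investigator", with sub-items for the median with its two-sided 95% CI and for event-free rates.

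TTR appears in one other place, the ad-hoc analysis list in SAP VI.G: "ORR, DOR, TTR, PFS per RECIST v1.1 by Investigator". It is not an endpoint in Protocol 2.2 or SAP IV, nor among the secondary efficacy endpoints that open SAP VIII.C. The SAP gives it no start date, event definition or risk set. Table 1a covers PFS and DOR, Table 1b covers iPFS and iDOR, and Table 1c covers OS.

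Two rules in SAP VIII.A bear on who can still respond. BOR is recorded only up to PD or death, and assessments made after new anticancer therapy do not count towards ORR or BOR.

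**The concern.** In a Kaplan-Meier analysis each subject either has the event or is censored, and censored subjects are assumed to have the same later chance of the event as those still at risk. For response, that assumption fails for a subject who has progressed, died or moved to other therapy. Under the SAP's own rules that subject's chance of a countable response is zero, so these are competing events.

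If they are censored, each later response is divided by a shrinking risk set and the curve rises above the proportion who actually responded. The report could then show a curve implying, say, close to half of subjects responding beside a confirmed ORR of one third. In a single-arm trial that error flatters the treatment. A median TTR could also be reported when fewer than half of the subjects responded.

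**Working it through.** **The plan's own figure.** The documents give no figure for TTR. The only design figure is the sample size, from "A historical ORR of 19% with pembrolizumab monotherapy in subjects with HNSCC", "An anticipated ORR of 35% with CMP-001 and pembrolizumab (alternative hypothesis" and "Power of 80% and one-sided alpha level of 0.05". By the normal approximation, n = [(1.645 × √(0.19 × 0.81) + 0.842 × √(0.35 × 0.65)) / 0.16]² = 42.8, rounded up to 43, which reproduces "A total of 43 subjects is planned for this study". It has no bearing on TTR except to supply a plausible range of ORR, 19% to 35%.

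**Inputs for the illustration.** N is 24 (SAP II.C: "The number of subjects included in this study is 24"). Scans are at Week 10 and every 9 weeks after (SAP VIII). All response and exit patterns below are assumptions.

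**Worked case.** Three subjects progress, die or start new therapy before Week 10. Week 10 has 6 responses, 8 PD and 7 stable. Week 19 has 2 responses and 3 PD, and 2 subjects remain.

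- Confirmed ORR = (6 + 2)/24 = 33.3%.
- Kaplan-Meier with the exits censored: at risk at Week 10 = 24 − 3 = 21, so S = 15/21 = 0.714. At risk at Week 19 = 7, so S = 0.714 × 5/7 = 0.510. One minus S = **49.0%**.
- Cumulative incidence with the exits as competing events: (21/24)(6/21) + (7/24)(2/7) = 6/24 + 2/24 = **33.3%**, equal to the ORR.
- Kaplan-Meier with non-responders held to the end of follow-up: S = (18/24)(16/18) = 16/24, so one minus S = 33.3%. There is no gap.

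**Other assumed patterns, N = 24, exits censored at the scan where they occur.**

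| Responders | Responses by scan | Exits by scan | ORR | 1 − KM |
|---|---|---|---|---|
| 5 | 3, 1, 1, 0, 0 | 9, 4, 2, 1, 1 | 20.8% | 31% |
| 5 | 2, 1, 1, 1, 0 | 9, 4, 2, 1, 1 | 20.8% | 41% |
| 8 | 5, 2, 1, 0, 0 | 8, 3, 2, 1, 1 | 33.3% | 46% |
| 8 | 4, 2, 1, 1, 0 | 8, 3, 2, 1, 1 | 33.3% | 55% |
| 8 | 8, 0, 0, 0, 0 | 8, 3, 2, 1, 1 | 33.3% | 33.3% |

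The last row is the second case without a gap: every response falls at the first scan and nobody leaves before it.

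**Simulation, N = 24.** Responses were split 75/20/5% over Weeks 10, 19 and 28. Non-responders left at Weeks 5, 10, 19, 28, 37 and 46 in proportions 10/45/20/10/8/7%. The mean of 1 − KM is about 27% at a true ORR of 19% and 47% at 35%. At 35%, a Kaplan-Meier median is reached in about 40% of trials, whereas at least half of the subjects respond in about 9%.

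A second set used a constant chance per scan over six scans (response 0.10 to 0.22, exit 0.30 to 0.40). It gave larger gaps: crude proportions of 22% to 38% against mean 1 − KM of 45% to 70%. The size therefore depends heavily on timing.

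**The responder-only reading.** If only confirmed responders are at risk, everyone in the curve has the event. It reaches 100% by construction, and its event-free rates describe timing among responders, not the chance of responding.

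**The case against.** The strongest objection is that the SAP nowhere says that progression or death is censored for TTR, or that all treated subjects are at risk. The lead-in naming the Treated Analysis Set also covers DOR, which sits in the same item and is restricted to confirmed responders by SAP VIII.A. The lead-in may therefore name only the source population. With a responder-only TTR there is nothing to overstate, and the median is the summary one would want anyway.

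Much of this stands. The risk set and the censoring are inferred from the named method and the stated population. But DOR carries an explicit restriction and TTR carries none, so the plain reading for TTR is all treated subjects. The responder-only reading also leaves event-free rates that cannot be read as a chance of response. A programmer could follow the text and produce either figure.

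Three stronger readings are tempting and are not supported:

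- A reader might infer that 1 − KM is bound to exceed the ORR. It is not, as the two no-gap cases show.
- A reader might infer that the same plot is planned for the ad-hoc analysis. SAP VI.G makes its displays summary tables unless stated otherwise. It lists TTR without a plot, and the Kaplan-Meier methods paragraph in VIII.C to which it would lead does not name TTR.
- A reader might treat 49% against 33% as a measured error. It illustrates one assumed pattern.

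**Conclusion.** The point holds as a missing specification with a likely bias. TTR has no definition, risk set or censoring rule, and the method named on the population named would usually give a curve above the confirmed ORR. Under the assumed patterns with 24 subjects the excess runs from none to about 22 points in the hand-set cases (55% against 33.3%), and averages 8 to 12 points in the first simulation and 23 to 32 in the second. These figures require all treated subjects at risk, censoring at exit, and some responses after other subjects have left.

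The consequence is small. TTR is not an endpoint, SAP II.C makes all analyses descriptive and exploratory, and the chance of responding is reported directly as confirmed ORR with a Clopper-Pearson interval, which this does not touch. The change is still worth making, because it avoids a figure that could contradict the primary result beside it.

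**What to change.** In SAP VIII.A, define TTR as the time from first dose to the first documented CR or PR in subjects whose response is later confirmed. Report n, median and range in those subjects, and remove TTR from the Kaplan-Meier item in VIII.C.

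If a curve in all treated subjects is wanted, specify the Aalen-Johansen cumulative incidence of confirmed response, with PD, death and new anticancer therapy as competing events and subjects still under assessment censored at the last scan. It ends at the ORR once follow-up is complete. Use the same TTR definition for the summary in VI.G.

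The cost is a few lines of SAP text and at most one changed figure. No new data are needed.

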5.1.2.3. CMP-001 Injections

5.1.2.3.1. Tumor Selection

Cutaneous, SC, and/or nodal tumors that are visible, palpable, or detectable by ultrasound guidance are acceptable for IT injection. Refer to [Appendix G](#) for CMP-001 injection guidelines.

Vigilance should be used when selecting lesions for injection that are in close proximity to critical structures (e.g., major airways).

Special attention and judgement should be exercised before injection of a lesion in the following areas: the "mask areas" of the face (central face, eyelids, eyebrows, periorbital nose, lips [cutaneous and vermillion], chin, mandible, preauricular and postauricular skin/sulci, temple, ear, genitalia, hands, and feet).

Tumors should be at least 0.5 cm in longest diameter and need not be the largest lesion. A visceral tumor may be injected with or without the use of interventional radiology if, in the opinion of the Investigator and after discussion with the Medical Monitor, it is the most appropriate site for IT injection. A preferred tumor for IT injection is an accessible lesion that is most rapidly progressing in the judgment of the Investigator.

When more than 1 tumor is amenable to IT injection, the Investigator may inject up to 3 tumors per CMP-001 treatment visit. The total dose of CMP-001 may be divided across the tumors at the Investigator's discretion, and the volume injected into each tumor must be recorded. The same tumor(s) should be injected each week during therapy, if possible. If an

injected tumor is clearly decreasing in size and another accessible non-injected tumor is not, then the Investigator may divide the CMP-001 dose between the 2 tumors or switch from injecting the regressing tumor to injecting the non-responding (or growing) tumor.

Subjects with metastatic disease who have regression of all injectable lesions, or who have an injection site reaction that precludes injection of the tumor, should receive CMP-001 SC near an original tumor (peritumoral) or in the area of the draining lymph nodes (see [Appendix G](#)).

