The performance of the statistical analysis for the exploratory efficacy endpoint is contingent on the availability of the data source. Given the response assessment based on itRECIST³ by Investigator has not been collected, and that the RECIST v1.1 and iRECIST were deemed sufficient for the purpose of the response assessment in the study from the Medical's perspective, no exploratory efficacy analyses will be carried out for the exploratory phase 2 study.

IX. Safety Analyses

Safety analyses will use data from the Treated Analysis Set. Subjects will be analyzed according to the actual study treatment received.

A. Exposure

Exposure to CMP-001 and Pembrolizumab will be summarized separately for the Treated Analysis Set with descriptive statistics for the number of doses received, the average number of volumes injected per dosing visit, the duration of treatment for each treatment (weeks), the planned dose intensity, the actual dose intensity, the relative dose intensity (%), and the treatment compliance.

1. Duration of Treatment

Regeneron Pharmaceuticals Inc. / Protocol: CMP-001-007
IQVIA Biotech (Confidential) Project # SZA56629

Duration of treatment (DoT) of CMP-001 and Pembrolizumab will be summarized in a descriptive manner, respectively. DoT will be calculated as follows:

$$\text{DoT (weeks)} = [\min(\text{last dose date} + 21 \text{ days, discontinuation/completion date}) - \text{first dose date}] / 7$$

2. Dosing Intensities

(1) Actual dose intensity (mg/week) will be calculated as the total actual cumulative dose received divided by duration of treatment (weeks) for CMP-001 and Pembrolizumab, respectively.

(2) Planned dose intensity (mg/week) will be calculated as the total planned cumulative dose to be received divided by the planned duration of treatment (weeks) based on the protocol schedule.

$$\text{Planned Duration of Treatment (weeks)} = \text{number of planned treatments} \\ * 3 \text{ weeks}$$

(3) Relative dose intensity (%) will be calculated based on the actual cumulative dose received relative to the planned cumulative dose throughout the duration of treatment as follows:

$$\text{Relative dose intensity (\%)} = (\text{actual dose intensity} / \text{planned dose intensity}) * \\ 100\%$$

3. Treatment Compliance

Treatment compliance is calculated as the number of CMP-001/Pembrolizumab doses received/expected doses within the treatment period defined as time from first dose to last dose.

4. Dosage Modifications

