The number of subjects with dose modifications (e.g., Drug Delayed, Drug Withheld, Drug interrupted, Dose Reduced, Drug Permanently Withdrawn) with the reasons will also be summarized by study drug.

Additionally, subgroup analysis of drug dosing and intensities for subjects by schedule will also be performed. Listings will be provided with the information from the study drug administration eCRFs for CMP-001 and Pembrolizumab, including date and time of each dose, route of administration, dose administered, location of each injection, and the volume injected into each tumor at each dosing visit.

Regeneron Pharmaceuticals Inc. / Protocol: CMP-001-007
IQVIA Biotech (Confidential) Project # SZA56629

B. Adverse Events

Adverse events should be recorded upon first occurrence and followed until resolution. A persistent AE is continuous and does not resolve between Q3W dosing visits; and should be documented only once unless the grade becomes more severe. If the grade becomes more severe, the AE must be reported again with the new grade. Any recurrent AE should be reported as new AE each time the AE occurs. Worsening of an ongoing TEAE (i.e., an increase to higher grade) should be recorded as a new AE. Ongoing AEs that decrease in severity/grade should not be captured as new AEs.

According to Protocol section 8.1.1, disease progression, and associated hospitalizations and deaths, are not considered an AE or SAE in this study.

Medical occurrences that begin before start of study treatment should be recorded on the Medical History/Current Medical Conditions section of the eCRF, not the AE section.

Adverse events starting more than 30 days after the last dose of study treatment should not be recorded on the AE eCRF unless they are related to study treatment.

Serious adverse events and AEs resulting in discontinuation will be followed until 1 of the following occurs:

- The event resolves
- The event stabilizes
- The event returns to a Baseline value if a Baseline value is available
- The event can be attributed to agents other than the study treatment or to factors unrelated to study conduct
- The Investigator and Medical Monitor agree that follow-up is no longer necessary

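### SAP IX.A.2 divides by a planned duration (planned treatments × 3 weeks) that need not equal the actual duration, so relative dose intensity can differ from 100% in fully adherent subjects

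*SAP*

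**What the plan says.** SAP IX.A reports dose intensity separately for CMP-001 and pembrolizumab.

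- **Duration of treatment (IX.A.1).** DoT runs from first dose to the earlier of two dates, min(last dose + 21 "days, discontinuation/completion date"), in weeks.
- **Actual intensity (IX.A.2(1)).** Actual cumulative dose divided by DoT.
- **Planned intensity (IX.A.2(2)).** "Planned dose intensity (mg/week) will be calculated as the total planned cumulative dose to be received divided by the planned duration of treatment (weeks". Planned duration is "number of planned treatments" × 3 weeks. There is no split by drug or schedule, and *treatments* is not defined.
- **Relative dose intensity (IX.A.2(3)).** In words, the "actual cumulative dose received relative to the planned cumulative dose throughout the duration of treatment". As a formula, actual intensity over planned intensity × 100%.
- **Compliance (IX.A.3).** "Treatment compliance is calculated as the number of CMP-001/Pembrolizumab doses received/expected doses", counted from first to last dose. It does not use planned duration.
- **Subgroups (IX.A.4).** A "subgroup analysis of drug dosing and intensities for subjects by schedule will also be performed".

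SAP VI.J.3 defines the schedules by consent version. On Schedule A, "subjects will receive CMP-001 10 mg weekly for 7 doses", then every 3 weeks from Week 10. Schedule B has 2 weekly doses, then every 3 weeks from Week 4. Subjects who re-consented from protocol v2.0 to v3.0 are placed in B. Pembrolizumab is 200 mg every 3 weeks throughout.

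**The concern.** A 3-week multiplier suits a drug given every 3 weeks. CMP-001 starts with a weekly phase, 7 doses on A and 2 on B. If each administration counts as 3 weeks, planned duration is too long, planned intensity too low and relative dose intensity too high, more so on A than on B. The planned by-schedule comparison would then show a difference in relative dose intensity that the formula creates.

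There is a second mismatch that does not depend on how *treatments* is read. DoT is shortened when a subject stops within 21 days of the last dose. Planned duration has no such rule.

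At stake is whether a reader can take 100% to mean that the planned dose was given, for either drug.

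**Working it through.** The documents give no planned or relative dose intensity figure, so there is none to reproduce. The check applies the SAP formulas to adherent subjects.

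**General form.** Let D be actual cumulative dose, D* planned cumulative dose, T the DoT and P the planned duration. Then

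relative dose intensity = (D/T) / (D*/P) = (D/D*) × (P/T).

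The verbal definition is D/D*. The formula therefore carries an extra factor P/T, and the two agree only when P = T.

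**Inputs.** CMP-001 10 mg per dose; A: W1 to W7, then W10, W13, …; B: W1, W2, W4, W7, …; pembrolizumab 200 mg at W1, W4, W7, … (SAP VI.J.3). Planned doses are counted up to the subject's own last dose.

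**Reading 1: treatments are administrations.** With k planned CMP-001 doses, P = 3k and planned intensity = 10k/3k = 3.33 mg/week on either schedule, whatever k is. If DoT ends 21 days after the last dose and T = 9, 12, 15, …:

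- A: k = 7 + (T − 9)/3, so P/T = 3k/T = 1 + 12/T
- B: k = 4 + (T − 9)/3, so P/T = 3k/T = 1 + 3/T

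| T (weeks) | Doses A / B | Actual intensity A / B (mg/week) | Relative dose intensity A / B |
|---|---|---|---|
| 9 | 7 / 4 | 7.78 / 4.44 | 233% / 133% |
| 24 | 12 / 9 | 5.00 / 3.75 | 150% / 112.5% |
| 54 | 22 / 19 | 4.07 / 3.52 | 122% / 106% |

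The verbal definition gives 100% in every cell. Missed doses are offset as well. At T = 24, 8 doses give 80/24 = 3.33 mg/week and so 100%, where the dose ratio is 8/12 = 67% on A and 8/9 = 89% on B. Pembrolizumab is right here: 1600/24 = 66.7 actual and 1600/(8 × 3) = 66.7 planned, 100%.

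**Reading 2: treatments are 3-week cycles.** At T = 24 there are 8 cycles, so P = 24. Planned intensity is 120/24 = 5.00 (A) and 90/24 = 3.75 (B), and both schedules show 100%. The Reading 1 errors are gone for subjects past the weekly phase.

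Now take an adherent subject last dosed at W7 who stops 7 days later. DoT is 6 + 1 = 7 weeks; planned duration is 3 cycles × 3 = 9 weeks.

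- CMP-001, B: actual 40/7 = 5.71, planned 40/9 = 4.44, giving 129%
- CMP-001, A: actual 70/7 = 10.00, planned 70/9 = 7.78, giving 129%
- Pembrolizumab: actual 600/7 = 85.7, planned 600/9 = 66.7, giving 129%

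In general, with c cycles started and a stop d days after a last dose given at the start of cycle c (d < 21), the factor is 3c/(3c − 3 + d/7). For d = 7 it is 9/7 = 129% at c = 3, 24/22 = 109% at c = 8 and 54/52 = 104% at c = 18. For c = 3 and d = 14 it is 9/8 = 112.5%.

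On Reading 1 the same early stop gives a B subject 5.71/3.33 = 171%.

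**The case against.** The strongest reply is that *treatments* was meant as 3-week cycles. IX.A says doses when it counts administrations, so a different word beside a 3-week multiplier may well mean a cycle. A full two-year plan points the same way. Counting administrations gives 39 × 3 = 117 weeks on A and 36 × 3 = 108 on B, against a two-year cap; 35 cycles give 105. On the other side, neither document defines a CMP-001 dosing cycle, and Protocol 5.1.2.3.1 uses the word for a single injection visit: "the Investigator may inject up to 3 tumors per CMP-001 treatment visit". The reading is open, so a reader who infers that the plan simply reports 150% or 233% goes further than the text allows. The reply does not rescue the rule, because the early-stop mismatch remains on the cycle reading and for both drugs.

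Three further inferences are not supported.

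- **Under-dosing would be concealed.** Number of doses and compliance are in the same exposure summary, and every dose is listed.
- **Schedule B subjects would be scored against 7 weekly doses, because SAP II.A describes only that schedule.** VI.J.3 defines both schedules by consent version, and II.A drives no calculation. This is clerical.
- **Re-consented subjects would be scored wholly on B.** VI.J.3 assigns only their subgroup. What is missing is a rule for counting their planned and expected doses; their number is not given.

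It is also fair to say that, with a CMP-001 dose fixed by Protocol 5.1.2.4, the corrected measure will lie close to compliance. That follows from the SAP's own verbal definition.

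**Conclusion.** Wrong as written, and minor. The formula departs from the SAP's verbal definition by the factor P/T, and on neither reading of *treatments* is that factor always 1 for adherent subjects.

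- **Administrations reading:** CMP-001 only, 1 + 12/T on A and 1 + 3/T on B. The distortion shrinks with longer treatment, and the by-schedule comparison of relative dose intensity partly reflects the formula.
- **Cycle reading:** correct after the weekly phase when DoT ends 21 days after the last dose, too high on both drugs when a subject stops sooner.

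The figures assume on-schedule dosing and planned doses counted to the subject's last dose. The A/B split and the stopping times are not in the documents, so no pooled figure can be given.

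One might infer that the whole A-B exposure comparison, or efficacy, is compromised. It is not. Actual dose intensity, number of doses and compliance do not use planned duration, and neither do ORR, DOR, PFS or OS. The effect is limited to planned and relative dose intensity in descriptive summaries of 24 subjects.

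**What to change.** For both drugs:

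1. Compute planned cumulative dose from the subject's own VI.J.3 schedule over exactly the DoT period, with the same min() end rule. Count doses due from the first dose up to, but not including, the end date.
2. Use that period as planned duration and delete the × 3 weeks rule. Relative dose intensity is then actual over planned cumulative dose, as IX.A.2(3) says in words. In the early-stop example it gives 40/40, 70/70 and 600/600, each 100%; at T = 24, 8 doses give 67% on A and 89% on B.
3. Take expected doses in IX.A.3 from the same schedule, from first to last dose.
4. For subjects re-consented from v2.0 to v3.0, count planned and expected doses under A before the date they switched schedule and under B after it.

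Defining *treatments* as 3-week cycles would not be enough, since it leaves the early-stop mismatch.

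The cost is a few lines of SAP text and one exposure derivation. Schedule is already derived for the subgroup tables. The only added item is a switch date for re-consented subjects.
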